16. APPENDICES

16.1. Appendix 1: Protocol Deviation Management and Definitions for Per Protocol Population

16.1.1. Exclusions from Per Protocol Population

A participant meeting any of the following criteria will be excluded from the Per Protocol population:

Number	Exclusion Description		
01	Participant did not receive at least 4 doses of study treatment		
02	Placebo participant received active treatment		
03	Participant did not participate in at least one post-dose assessment		
04 ^[1]	Participant excluded on basis of final review of inclusion/exclusion criteria		
05 ^[1]	Participant excluded on basis of final review of the prohibited medication use		
^[1] Note: Da	^[1] Note: Data reviewed and decisions regarding exclusions from the Per Protocol population will be		

201247

16.2. Appendix 2: Schedule of Activities

16.2.1. Protocol Defined Schedule of Activities

The following SOA tables are taken from protocol amendment 4 and are included in the RAP for convenience.

Note that baseline ECG is a triplicate measurement; see Appendix 6.

16.2.1.1. Screening

Procedure	Screening (between -42 and -1 days)	Notes
Informed Consent	Х	The screening period for women of child bearing potential
Inclusion and Exclusion Criteria	Х	(WOCBP) must be at least 28 days to allow for a 28 day interval between the screening and Day 1 pregnancy tests.
Demographics	Х	
Complete Physical Exam	Х	See Appendix 1 for abbreviations.
Medical History	Х	1. Respiratory laboratory FVC will be used for study eligibility
mRSS	Х	and will be entered into the eCRF.
Respiratory Laboratory FVC1	Х	2. The participant will be trained in FVC measurement using a band held device. The first set of trinlicate readings will be
Home spirometry FVC ²	Х	recorded by the participant at the clinical site. Thereafter
DLCO - corrected for haemoglobin	Х	approximately weekly measurements will be collected by the
Concomitant Medications	Х	participant and entered into a paper diary. 3 OuantiFERON-TB Gold PLUS test is also acceptable
12 lead ECG - single measurement	Х	
Vital Signs (blood pressure, heart rate, body temperature)	Х	
QuantiFERON-TB Gold test ³	Х	
Serum Pregnancy Test (WOCBP only)	Х	
Oestradiol + FSH (as needed see Appendix 2)	Х	
HIV, Hepatitis B and Hepatitis C	Х	
Standard Haematology / Clinical Chemistry / Urinalysis (listed in Appendix 2)	Х	
Additional Haematology (listed in Appendix 2)	Х	
CRP	Х	
SAE - commencing from time of informed consent	Х	

201247

16.2.1.2. Treatment period and follow-up

Procedure		ent Period	(Days)	i.						M	al13 2)
		Day 15 ±2 days	Day 29 ±2 days	Day 43 ±2 days	Day 57 ±2 days	Day 71 ±3 days	Day 85 ± 3 days	Day 113 ±5 days	Day 155 ±10 days	Day 197 ± 10 days (Final Follt –Up)	Early Withdraws (refer Section 8
Study Week	-	W2	W4	W6	W8	W10	W12	W16 ¹³	W2213	W2813	
Study Treatment	4	ļ			1			1		ι	
Randomisation	X1										
Study Treatment Administration	Х	Х	Х	Х	Х	Х					
Baseline Assessments											
Autoantibodies	X1										
Medical History ²	Χ1										
Safety Assessments and Cardiac Monitoring				,	,		,	,	,	p	,
Complete Physical Exam	X1									Х	Х
Brief Physical Exam		Х	Х	Х	Х	Х	Х	Х	Х		
Vital Signs (blood pressure, heart rate, temperature)	χ1	Χ1	X1	X1	X1	X1	Х	Х	Х	Х	Х
12 -lead ECG (triplicate at day 1 or if QTc abnormal)	X1	X1			X1						
E/SAE Review ^{3, 13} Continuous throughout study											
Concomitant Medication Review ¹³	oncomitant Medication Review ¹³ Continuous throughout study										
Serum Pregnancy Test (WOCBP) ¹³										X14	X14
Urine Pregnancy Test (WOCBP) ¹³	X1	X1	X1	X1	X1	X1	Х	Х	X		
Standard Haematology/Clinical Chemistry (see Appendix 2)13	X1, 4	X	Х	Х	Х	Х	X4	X	Х	Х	Х
Additional Haematology (see Appendix 2 for list)	X1						Х			Х	Х
Urinalysis	X1						Х			Х	Х
Pharmacokinetics, Pharmacodynamics, Immunogenicity and Gen	etics										
Optional Suction Blister ⁵					←	X					
Immunogenicity Sampling	X1	Х			Х		Х			Х	Х
Pharmacokinetic Blood Sampling	X1	Х	Х		Х		Х	Х	X	Х	Х
Target Engagement (OSM) Blood Sampling	X1	Х	Х		Х		Х	Х	Х	Х	Х
Genetic Sampling ⁶	Х										
Disease markers (efficacy) Assessment											
Skin Biopsy	X1						Х 7				X8
Blood Biomarkers (see Section 9.8.1)	X1,9		Х		Х		Хa			Х	
C-reactive protein (CRP)	X1	Х	Х		Х		Х	Х		Х	Х
mRSS	X1				Х		Х			Х	X ¹⁰
Respiratory Laboratory FVC	X1						Х			Х	X10
Home Spirometry FVC11		<			W	eekly			>		
SHAQ /PhGA//PtGA/CRISS data12	X1						Х			Х	

201247 | Statistical Analysis Plan RAP Amendment 3 Final_V1 21 Aug 2020 | TMF-2068612 | 1.0

CONFIDENTIAL

201247

1. To be performed pre-dose.

2. Medical history will include smoking history and information regarding the participant's most recent HRCT scan if available. Medical occurrences that begin before the start of study treatment (Day 1) but after obtaining informed consent will be recorded as medical history.

3. SAEs will be recorded from signing of informed consent; AEs will be recorded from administration of first study treatment.

4. Day 1 predose sample and Day 85 (Week 12) will be fasted and include lipid assessments.

5. Suction blister is an optional procedure for cohort 2 and additional consent will be required. Suction blister will only be performed once per participant (at anytime from the Day 57 (Week 8) visit to the Day 85 (Week 12) visit inclusive) at selected sites

6. Genetics sampling is an optional assessment and additional consent will be required. Genetic sample can be taken any time after randomisation.

7. Skin biopsy scheduled for Day 85 (Week 12) may be taken on an alternative day to the rest of the assessments, but must remain within the Day 85 (Week 12 ± 3 days) time window. 8. Skin biopsy only performed if the early withdrawal visit occurs on or after the Day 57 (Week 8) visit but before when the Day 85 (Week 12) visit would have been scheduled and the participant is willing.

9. At the Day 1 and Day 85 (Week 12) visits, additional blood volume is required for possible proteomic and transcriptomic analyses.

10. Respiratory Laboratory FVC and mRSS will only be performed if the early withdrawal visit occurs on or after the Day 57 (Week 8) visit.

11. Home spirometry FVC measured weekly by the participant via a hand held device, until the Day 197 (Week 28) visit.

12. Data to support CRISS calculation will be collected at Day 1, Day 85 (Week 12) and Day 197 (Week 28).

13. If an on-site visit is not possible due to the COVID-19 pandemic, a virtual or telephone visit can be performed for any study assessments that can be conducted remotely (e.g., AE/SAE review & concomitant medication review). In these circumstances, scheduled safety (standard hematology and clinical chemistry) labs and pregnancy tests should be

performed if feasible and may be performed locally at the clinical site or within the community (all at the discretion of the Investigator).

14. If it is not possible for a serum pregnancy test to be performed due to the COVID-19 pandemic, a urine pregnancy test should be performed if possible.

201247

16.3. Appendix 3: Assessment Windows

Following visit windows are applied for early withdrawal and unscheduled visits. The target day is the planned analysis timepoint and windows have been constructed with limits approximately equally spaced between visits. If more than one values within analysis timepoint with equal distance from the target day then average will be used.

Table A:

Domain	Analysis Window	Analysis	
	Beginning Timepoint	Ending Timepoint	Timepoint
All	Day 1	Day 1	Day 1
Vital Signs, Standard	Day 8	Day 22	Day 15
Haematology/Clinical Chemistry	Day 23	Day 36	Day 29
	Day 37	Day 50	Day 43
	Day 51	Day 64	Day 57
	Day 65	Day 78	Day 71
	Day 79	Day 99	Day 85
	Day 100	Day 134	Day 113
	Day 135	Day 176	Day 155
	Day 177	> Day 197	Day 197
Additional Haematology, Urinalysis,	Day 68	Day 99	Day 85
Laboratory FVC, SHAQ-VAS, HAQ-DI, PhGA, PtGA and CRISS	Day 145	> Day 197	Day 197
Immature Reticulocyte Fraction	Day 37	Day 50	Day 43
	Day 68	Day 99	Day 85
	Day 145	> Day 197	Day 197
ECG	Day 8	Day 22	Day 15
	Day 50	Day 64	Day 57
Target Engagement (OSM)	Day 8	Day 22	Day 15
	Day 23	Day 43	Day 29
	Day 50	Day 64	Day 57
	Day 78	Day 92	Day 85
	Day 108	Day 120	Day 113
	Day 145	Day 165	Day 155
	Day 187	> Day 197	Day 197
Blood Biomarkers	Day 15	Day 43	Day 29
	Day 44	Day 71	Day 57
	Day 72	Day 99	Day 85
	Day 145	> Day 197	Day 197
CRP	Day 8	Day 22	Day 15
	Day 23	Day 43	Day 29
	Day 44	Day 71	Day 57

201247

Domain	Analysis Window	Analysis	
	Beginning Timepoint	Ending Timepoint	Timepoint
	Day 72	Day 99	Day 85
	Day 100	Day 127	Day 113
	Day 145	> Day 197	Day 197
mRSS	Day 43	Day 71	Day 57
	Day 72	Day 99	Day 85
	Day 145	> Day 197	Day 197
Skin Biopsy	Day 55	Day 99	Day 85
Home FVC ^[1]	Day 5	Day 11	Day 8
(Target visit -/+ 3 days)	Day 12	Day 18	Day 15
	> Day 194		Day 197

[1] Steps for Home FVC Slotting

- Step 1: Select maximum value within a day.
- Step 2: After slotting, select the closest target day.
- Step 3: If more than one value within the analysis timepoint with equal distance from the target day, the 'average of maximum value' will be used.

For PK, planned assessments will be summarised, unscheduled assessments will be listed. PopPK and PK/PD modelling will use all available data and will use actual relative time, not planned relative time.

Note: Following assessment window followed for all SRT reporting.

For safety, planned assessments will be summarised. Unscheduled and early withdrawal visits are included following the visit slotting algorithm for worst case or CTCAE grade summaries and figures. If more than one visit slots to the same analysis timepoint, the 'worst' case will be included in the summary and figure.

201247

Table B:

Analysis Set /	Target	Analysis	Analysis	
Domain		Beginning Timepoint	Ending Timepoint	Timepoint
Safety/ Haematology	The target day is the planned analysis timepoint. The windows	Days less than 0		Screening
	have been constructed with limits	Day 1	Day 1	Day 1
approximately equally spaced	Day 2	Day 22	Day 15	
		Day 23	Day 36	Day 29
		Day 37	Day 50	Day 43
		Day 51	Day 64	Day 57
		Day 65	Day 78	Day 71
		Day 79	Day 99	Day 85
		Day 100	Day 134	Day 113
		Day 135	Day 176	Day 155
		Day 177	Day 209	Day 197

201247

16.4. Appendix 4: Study Phases and Treatment Emergent Adverse Events

16.4.1. Study Phases

In general, assessments and events will be classified according to the time of occurrence relative to study treatment start date. Specific rules for Concomitant Medications and Adverse Events are specified in the section below.

Treatment Phase	Definition
Pre-Treatment	Date < Study Treatment Start
On-Treatment	Study Treatment Start ≤ Date ≤ Study Treatment Stop Date +28 days
Follow up	Study Treatment Stop Date +28 days < Date

16.4.1.1. Study Phases for Concomitant Medication

Non-systemic sclerosis medications taken prior to and not ongoing at the screening visit were not captured for this study.

Concomitant Systemic sclerosis medications and systemic sclerosis medication history (prior treatments) are captured separately in the eCRF and reported separately.

201247

16.5. Appendix 5: Data Display Standards & Handling Conventions

16.5.1. Reporting Process

Reporting Process					
Software					
The currently sup	ported versions of SAS	software will be used.			
Reporting Area					
HARP Server	: \\uk1salx00175.corpnet2.com				
HARP Areas	Compound: GSK2330	811			
	Study: MID201247				
	Reporting efforts: inter	rnal_ nn , Final where nn = nu	imber of each reporting		
	effort, following HARP	standard. The planned ide	entity of each 'internal'		
	Penarting effort		HAPD folder / PE		
	(RE) name in RAP	Туре	name		
	SRT1	Pre-programming/ dry run	srt 01		
	SRT1	Final	 srt 02		
	DEC	Dry run	 data_look_01		
	DEC	Final	safety_02		
	SRT2	Pre-programming/ dry run	data_look_02		
	SRT2 Final srt_03				
	IA1 Pre-programming/ dry run data_look_0		data_look_02		
	IA1	I Final safety_03			
	SRT3	Pre-programming/ dry run	data_look_03		
	SRT3 Final srt_04		srt_04		
	IA2	Pre-programming/ dry run	data_look_03		
	IA2	Final	safety_04		
	SRT4	Pre-programming/ dry run	data_look_04		
	SRT4	Final	srt_05		
	SRT5	Final	srt_06		
	SRT6	Final	srt_07		
	Adhoc DRC	Final	safety_05		
	SRT7	Final	srt_08		
	SAC	Pre-programming/ dry run	data_look_04		
	SAC Final Final				
	Note: SRTs or DRCs n numbering in the table maintained by S&P du prior to the final reporti	nay be called on an ad-hoc bas above. An up-to-date list of this ring study conduct and the table ng effort.	is which will affect the mapping will be above will be updated		
QC Spreadsheet	For each reporting effor : \\uk1salx00175.corpr	ort will be located: net2.com			

201247
Reporting Process
\arenv\arwork\gsk2330811\mid201247\ [reporting effort]\documents
Analysis Datasets
Analysis datasets will be created according to Legacy GSK A&R dataset standards.
Generation of RTF Files
• RTF files will be generated for tables at IA2 and Adhoc DRC and final reporting efforts.

Descriptive Summa	ry Statistics			
Continuous Data (normally distributed)	Refer to IDSL Statistical Principle 6.06.1			
Descriptive Summary Statistics (Skewed data)	N, n, geometric mean, standard deviation (SD) of logged data, between geometric coefficient of variation (CVb (%)), median, minimum and maximum will be reported.			
	Log base e data: CVb (%) = $\sqrt{(\exp(SD^2) - 1) * 100}$ [NOTE: SD = SD of log base 'e' transformed data]			
	Log base 2 data: CVb (%) = $\sqrt{(\exp(\log_e(2)^2 \text{ SD}^2) - 1) * 100}$ [NOTE: SD = SD of log base 2 transformed data]			
	Log base 10 data: CVb (%) = $\sqrt{(\exp(\log_e(10)^2 \text{ SD}^2) - 1) * 100}$ [NOTE: SD = SD of log base 10 transformed data]			
Descriptive Summary Statistics (Non-parametric data)	N, median, interquartile range (IQR), minimum, maximum			
Categorical Data	N, n, frequency, %. N = the number of participants from the relevant analysis population for the group or sub group. n = the number of participants counted for the summary statistic.			
Reporting of Pharm	acokinetic Concentration Data			
Descriptive Summary Statistics	Refer to IDSL Statistical Principle 6.06.1 Assign zero to NQ values (Refer to GUI_51487 for further details)			
Reporting of Pharm	acokinetic Parameters			
Descriptive Summary Statistics (Log Transformed)	No pharmacokinetic parameters will be summarised in this study, they will be produced for each participant from the population PK model and the typical value of model parameters is considered the appropriate summary.			
Graphical Displays				
Refer to IDSL Sta	atistical Principles 7.01 to 7.13.			
 For individual line subjects not on N will be given in th 	 For individual line plots, subjects on MMF at day 1 will be represented with a solid line and subjects not on MMF represented with a dashed line. The auto-antibody status of the subject will be given in the legend as per Section 6.1. 			

201247

16.5.3. Reporting Standards for Pharmacokinetics

Pharmacokinetic Con	centration Data
Descriptive Summary Statistics, Graphical Displays and Listings	Refer to IDSL PK Display Standards. Refer to IDSL Statistical Principle 6.06.1. Note: Concentration values will be imputed as per GUI_51487 for descriptive summary statistics/analysis and summarized graphical displays only.
NONMEM/Pop PK File	Pop-PK file (CSV format) for the POP-PK analysis by Clinical Pharmacology Modelling and Simulation function will be created according to the data specification detailed in Section 16.9.1 Pharmacokinetic / Pharmacodynamic Dataset Specification
NONMEM/PK/PD File	PK/PD file (CSV format) for the PK/PD analysis by Clinical Pharmacology Modelling and Simulation function will be created according to the data specification detailed in Section 16.9.1 Pharmacokinetic / Pharmacodynamic Dataset Specification
Pharmacokinetic Para	ameter Derivation
PK Parameter to be Derived by Programmer	Highest Concentration – Measured concentration in post dose till the time of nadir. Steady State – Measured concentration before the last administered dose.
Pharmacokinetic Para	ameter Data
Is NQ impacted PK Parameters Rule Being Followed	No.
Descriptive Summary Statistics, Graphical Displays and Listings	Refer to IDSL PK Display Standards.

201247

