Baseline Assessments												
Autoantibodies	X ¹											
Medical History ²	X ¹											
Safety Assessments and Cardiac Monitoring												
Complete Physical Exam	X ¹										X	X
Brief Physical Exam		X	X	X	X	X	X	X	X			
Vital Signs (blood pressure, heart rate, temperature)	X ¹	X ¹	X ¹	X ¹	X ¹	X ¹	X	X	X	X	X	X
12 –lead ECG (triplicate at day 1 or if QTc abnormal)	X ¹	X ¹			X ¹							
AE/SAE Review ^{3, 13}	Continuous throughout study											
Concomitant Medication Review ¹³	Continuous throughout study											
Serum Pregnancy Test (WOCBP) ¹³											X ¹⁴	X ¹⁴
Urine Pregnancy Test (WOCBP) ¹³	X ¹	X ¹	X ¹	X ¹	X ¹	X ¹	X	X	X			
Standard Haematology/Clinical Chemistry (see Appendix 2) ¹³	X ^{1, 4}	X	X	X	X	X	X ⁴	X	X	X	X	X

2016N269831_05

CONFIDENTIAL

201247

Procedure	Treatment Period (Days)							Day 113 ± 5 days	Day 155 ± 10 days	Day 197 ± 10 days (Final Follow -Up)	Early Withdrawal ¹³ (refer Section 8.2)
	Day 1	Day 15 ± 2 days	Day 29 ± 2 days	Day 43 ± 2 days	Day 57 ± 2 days	Day 71 ± 3 days	Day 85 ± 3 days				
Study Week		W2	W4	W6	W8	W10	W12	W16 ¹³	W22 ¹³	W28 ¹³	
Additional Haematology (see Appendix 2 for list)	X ¹						X			X	X
Urinalysis	X ¹						X			X	X
Pharmacokinetics, Pharmacodynamics, Immunogenicity and Genetics											
Optional Suction Blister ⁵					←-----X-----→						
Immunogenicity Sampling	X ¹	X			X		X			X	X
Pharmacokinetic Blood Sampling	X ¹	X	X		X		X	X	X	X	X
Target Engagement (OSM) Blood Sampling	X ¹	X	X		X		X	X	X	X	X
Genetic Sampling ⁶	X										
Disease markers (efficacy) Assessment											
Skin Biopsy	X ¹						X ⁷				X ⁸
Blood Biomarkers (see Section 9.8.1)	X ^{1,9}		X		X		X ⁹			X	
C-reactive protein (CRP)	X ¹	X	X		X		X	X		X	X
mRSS	X ¹				X		X			X	X ¹⁰
Respiratory Laboratory FVC	X ¹						X			X	X ¹⁰
Home Spirometry FVC ¹¹	←-----weekly-----→										
SHAQ /PhGA/PtGA/CRIS data ¹²	X ¹						X			X	

2016N269831_05

CONFIDENTIAL

201247

1. To be performed pre-dose.
2. Medical history will include smoking history and information regarding the participant's most recent HRCT scan if available. Medical occurrences that begin before the start of study treatment (Day 1) but after obtaining informed consent will be recorded as medical history.
3. SAEs will be recorded from signing of informed consent; AEs will be recorded from administration of first study treatment.
4. Day 1 predose sample and Day 85 (Week 12) will be fasted and include lipid assessments.

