5. STUDY DESIGN

5.1. Overall Design

This is a multi-centre, randomised, double blind (sponsor open), placebo-controlled, repeat-dose, proof of mechanism study of subcutaneous administrations of GSK2330811 in males and females with dcSSc.

The study includes two sequential cohorts. Cohort 1 is planned to consist of at least 4 participants and will evaluate a repeat-dose predicted to provide sub-maximal inhibition of OSM, leading to a dose escalation decision once at least 4 participants have reached the end of the treatment period (see Section 7.2). Cohort 2 will then evaluate a repeat-dose, predicted to provide maximal inhibition of OSM, to test POM. The study design, for both cohorts, is depicted in Figure 1.

Figure 1 Study Schematic

- Participants who consent will attend the clinical facility for screening and if eligible will enter the treatment period of the study within 42 days.
- The screening period will be at least 28 days for WOCBP to allow for a minimum 28 day interval between the screening and Day 1 pregnancy tests.
- Participants will be randomised in a 3:1 ratio within each cohort to GSK2330811 and placebo respectively. In cohort 2 treatment allocation will be stratified according to mycophenolate concomitant medication status (treated or non-treated).
- Participants will attend the clinical facility to receive a subcutaneous dose of GSK2330811 or placebo on Day 1 and then every other week until the sixth and final dose at the Day 71 (Week 10) visit.
- A Data Review Committee (DRC) will be responsible for determining progression from cohort 1 to cohort 2 as described in Section 7.2.
- Interim analyses will be conducted during cohort 2. The rationale, conduct and potential outcomes of these are described in Section 10.3.3.
- Study safety monitoring will be undertaken in a blinded manner by the Sponsor Safety Review Team (SRT) as described in Appendix 3. The Study Medical Monitor will also continuously review adverse events and laboratory tests for individual participants during the conduct of the study to ensure individual participant monitoring.
- Skin biopsies will be collected to assess GSK2330811 pharmacology and biomarkers at the site of action. Two punch biopsies will be collected from involved skin, on the forearm of participants, on both Day 1 and during the Day 85 (Week 12) visit window.

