5.5. Dose Justification

Dose levels for this study have been selected on the basis of PK/PD predictions, data from the first time in human study with GSK2330811 and preclinical data. Two dose levels (a 100 mg sub-maximal dose to test initial safety and tolerability and a 300 mg maximal dose to test POM) have been selected based on predicted target engagement after repeat dosing.

An in-vivo affinity of approximately 0.6 nM was estimated from first time in human data. The typical GSK2330811 apparent distribution volume was 11.5 L (95% Confidence Interval (CI): 10.2-13.1) and the typical apparent systemic clearance was 14.1 mL/hr (95% CI: 12.7-15.6). The mean terminal half-life ranged between 19 and 25 days. The ratio of GSK2330811 mean concentration between skin blister fluid and plasma ranged from 19 to 45%.

A target-mediated drug disposition (TMDD) model (Mager, 2005) using a one-compartment PK model together with binding kinetics of drug and target was developed to predict target engagement after repeat dosing.

First cohort: 100 mg every other week is considered a sub-maximal pharmacologically active dose with a predicted target engagement of approximately 80% in serum at trough.

Second cohort: 300 mg is predicted to achieve engagement of greater than 90% of OSM in serum at trough.

In addition a PKPD model was developed to assess the relationship between drug concentration and platelet count reduction [Wang, 2010] including a feedback mechanism. According to the model predictions after repeat dosing at 100 mg every other week, no participant is anticipated to achieve a CTCAE grade 2 or greater reduction in platelet count.

The NOAEL in the 13 weeks cynomolgus monkey study was 300 mg/kg/week. The PK exposure achieved in cynomologous monkey was more than 100 times greater than the predicted PK exposure in human (steady state AUC 21300ug.h/mL and Cmax 68.2ug/mL) at a dose of 300 mg every other week [GlaxoSmithKline Document Number 2016N284919_00].

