9. PHARMACOKINETIC ANALYSES

Pharmacokinetic data will be presented in graphical and/or tabular form and will be summarized descriptively. All pharmacokinetic data will be stored in the Archives, GlaxoSmithKline Pharmaceuticals, R&D.

Correlation analysis will be performed and presented as scatter plots including Pearson correlation coefficient for Measured Steady State Concentration vs Baseline Body Weight, Haemoglobin and Platelet Nadirs as Percentage Change from Baseline vs Measured Highest Concentration by treatment groups.

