16.12.8. Pharmacokinetic Tables

Pharma	Pharmacokinetic: Tables							
No.	Population	IDSL / TST ID / Example Shell	Title	Programming Notes	Deliverable			
PK Plas	sma Concentra	tion						
4.1.	РК	PKCT1	Summary of Plasma GSK2330811 Concentration-Time Data (ng/mL)	Add footnotes " Note: No. of subjects with results below the lower limit of quantification, assigned 0 (LLQ=100 ng/mL). SD is set to missing if No. Imputed/n > 0.3 Samples from Day 14 – Day 84 are taken at trough (2 weeks after dosing)."	DEC, IA1, IA2, Adhoc DRC, SAC			

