16.12.9. Pharmacokinetic Figures

Pharmacokinetic: Figures						
No.	Population	IDSL / TST ID / Example Shell	Title	Programming Notes	Deliverable	
PK Plas	sma Concentra	tion				
4.1.	PK	PKCF1P	Individual GSK2330811 Plasma Concentration-Time Plot by Subject (Linear and Semi-Log)	Footnote for all PK and PK/PD figures: Note: No. of subjects with results below the lower limit of quantification, assigned 0 (LLQ=100 ng/mL). Samples from Day 14 – Day 84 are taken at trough (2 weeks after dosing). Use actual time (days) as x axis (where days is a continuous variable)	DEC ^[1] , SAC	
4.2.	РК	PKCF1P	Individual GSK2330811 Plasma Concentration-Time Plot by Treatment (Linear and Semi-Log)	Use actual time (days) as x axis (where days is a continuous variable) [difference between this and 4.1 is that all profiles will be on one page for each treatment group] Note: No. of subjects with results below the lower limit of quantification, assigned 0 (LLQ=100 ng/mL). Samples from Day 14 – Day 84 are taken at trough (2 weeks after dosing).	IA1 ^[1] , IA2 ^[1] , Adhoc DRC, SAC	
4.3.	PK	PKCF4	Mean (\pm SD) Plasma GSK2330811 Concentration-Time Plots by Treatment (Linear and Semi-log)	Use planned time (days) as x axis (where days is a continuous variable)	IA1, IA2, SAC	
4.4.	РК	PKCF5	Median (Range) Plasma GSK2330811 Concentration-Time Plots by Treatment (Linear and Semi-log)	the lower limit of quantification, assigned 0 (LLQ=100 ng/mL). Samples from Day 14 – Day 84 are taken at trough (2 weeks after dosing).	SAC	

201247

Pharmacokinetic: Figures							
No.	Population	IDSL / TST ID / Example Shell	Title	Programming Notes	Deliverable		
4.5.	РК	201246/adhoc/ Figure 4.9	Mean (±SD) Plasma GSK2330811 Concentration-Time Plots grouped by Treatment (Linear and Semi-log)	As Figure 4.3 but on a single page , grouped by treatment. Add footnote Note: No. of subjects with results below the lower limit of quantification, assigned 0 (LLQ=100 ng/mL). Samples from Day 14 – Day 84 are taken at trough (2 weeks after dosing).	IA1, IA2, Adhoc DRC, SAC		
4.6.	РК	PK_F1	Scatter Plot of Individual Measured Steady State Concentration vs Baseline Body Weight	Panel by treatment group and grouped by individual subjects. X-axis Label: Body Weight (kg) Y-axis Label: Measured Steady State Concentration (ng/mL)	Adhoc DRC, SAC		

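### The 'measured steady state' concentration behind SAP Figure 4.6 is in practice a Day 57 or earlier trough, so the axis is mislabelled and participants at different dose stages are mixed

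*SAP*

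**What the plan says.** SAP section 16.5.3 (Reporting Standards for Pharmacokinetics) has the programmer derive a Steady State value as "Measured concentration before the last administered dose". SAP section 9 plans a Pearson correlation and scatter plot of "Measured Steady State Concentration vs Baseline Body Weight" by treatment group. SAP section 16.12.9 lists the display as Figure 4.6, in the PK population, for the ad hoc Data Review Committee review and the final analysis. Its y-axis label calls the value a measured steady-state concentration.

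Protocol section 5.1 has dosing every other week "until the sixth and final dose at the Day 71 (Week 10) visit". In the protocol's Schedule of Activities (section 2), the row "Pharmacokinetic Blood Sampling" has entries on Days 1, 15, 29, 57, 85, 113, 155 and 197 and at early withdrawal. The Day 43 and Day 71 cells are empty. The SAP repeats this schedule in section 16.2.1.2.

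The footnote to SAP Table 4.1 says that samples from Day 14 to Day 84 (counted from first dose, so study Days 15 to 85) "are taken at trough (2 weeks after dosing").

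**The concern.** The derivation presupposes a sample just before the last dose, and the schedule has none for anyone who receives the Day 71 dose. Read as the last available sample before the last dose, the rule gives Day 57, after four doses. Read as the pre-dose sample at the last dosing visit, it gives nothing for a completer.

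The rule also ties the sample to each participant's own last dose, so an early stopper contributes a value from an earlier stage of accumulation. The PK population does not screen these participants out. It needs only an active dose and an analysed sample (SAP section 4). The four-dose minimum in SAP section 16.1.1 belongs to the Per Protocol population. The SAP gives no rule for early stoppers or withheld doses in this variable.

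At stake is whether a reader can take the y-axis of Figure 4.6 at face value, and whether the coefficient reflects body weight alone or partly the number of doses received.

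**Working it through.** **Inputs.** All are from protocol section 5.5 unless stated.
- Half-life: "The mean terminal half-life ranged between 19 and 25 days".
- Apparent clearance 14.1 mL/hr; apparent volume 11.5 L.
- Stated steady-state AUC at 300 mg every other week: 21300 ug.h/mL.
- Dosing interval 14 days; doses on Days 1, 15, 29, 43, 57 and 71 (protocol section 2).

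**Reproducing the plan's own figure.** AUC at steady state = dose / (CL/F) = 300 mg / 14.1 mL/h = 21277 ug.h/mL, within 0.2% of the stated 21300. Half-life from the typical values = ln 2 × 11.5 L / 14.1 mL/h = 23.6 days, inside the stated range. The inputs agree with each other.

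**Which sample the rule selects.** Dosing is assumed uninterrupted up to the last dose.

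| Last dose given | Last scheduled PK sample before it | Doses behind that sample |
|---|---|---|
| Day 71 or Day 57 | Day 57 | 4 |
| Day 43 or Day 29 | Day 29 | 2 |
| Day 15 | Day 15 | 1 |
| Day 1 | Day 1 pre-dose | 0 |

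A Day 1 pre-dose sample would normally be non-quantifiable, and SAP section 16.5.2 assigns zero to such values in PK concentration summaries.

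**Fraction of steady-state trough.** With linear one-compartment kinetics, the trough after n doses every 14 days is 1 − 2^(−14n/T) of steady state, where T is the half-life in days.

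| Trough | Doses | T = 25 | T = 23.6 | T = 19 |
|---|---|---|---|---|
| Day 15 | 1 | 32% | 34% | 40% |
| Day 29 | 2 | 54% | 56% | 64% |
| Day 57 | 4 | 79% | 81% | 87% |
| Day 71 (not sampled) | 5 | 86% | 87% | 92% |
| Day 85 | 6 | 90% | 92% | 95% |

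For example, Day 57 at T = 25 is 1 − 2^(−56/25) = 0.788. The ±2 day window at Day 57 widens its range to 78-88%. Adding first-order absorption, with the rate fitted so that the model returns the stated Cmax of 68.2 ug/mL, changes these fractions by no more than 0.2 percentage points.

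**Effect on the correlation.** Pearson's r does not change when every value is multiplied by one factor, so a shortfall common to completers has no effect. What matters is the gap between an early stopper and the other plotted points. A Day 29 value is 0.540/0.788 = 69% (T = 25) to 0.640/0.870 = 74% (T = 19) of a Day 57 value.

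The documents give no between-participant variability, so this step rests on an assumed concentration CV of 20-40% and weight CV of about 20%. In simulated sets of 15 active participants (the cohort 2 number in protocol Table 3), multiplying one value by 0.69 moved r by a median of 0.03-0.07, with a 95th percentile of 0.12-0.23. The sampling SD of r at that size is already 0.21-0.27.

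**The case against.** The case against acting is that this is one descriptive scatter plot with no hypothesis attached. SAP section 16.5.2 says no PK parameters will be summarised. Steady-state exposure is taken from the population model as an individual predicted AUC (SAP section 10.1.1.2), which uses actual dose and sample times. Body weight is in the modelling dataset (SAP section 16.9.1). The protocol also allows PK time points to be altered (section 2), so an unscheduled Day 71 sample is possible. All of this stands, and it keeps the point small.

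The objection also disposes of several stronger readings that a reader might infer:
- *That the plotted values are far below steady state throughout.* For completers the shortfall is 13-21%. A Day 71 sample would itself reach only 86-92%, so its absence costs about 5-7 percentage points. A large gap arises only for early stoppers.
- *That the Day 85 trough is collected and ignored.* It is in Table 4.1, in Figures 4.1 to 4.5 and in the population modelling. It is left out of this one variable.
- *That one early stopper would drive the body-weight correlation.* The usual shift is small against sampling error. Several stoppers, or a zero from someone dosed only on Day 1, would matter more. In the 100 mg group, planned at three active participants, r is uninterpretable under any definition.

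The objection does not rescue the definition itself. The label says steady state, the schedule cannot supply it under the stated rule, and a later trough is available.

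**Conclusion.** The point holds as a minor one. As written, the rule returns a Day 57 trough for completers (79-87% of steady state) and a Day 29 or earlier value for anyone whose last dose was Day 43 or earlier (54-64% or less). Figure 4.6 is therefore mislabelled, and its coefficient mixes dose stages. The documents do not support going further: the completers' shared shortfall does not bias r, the typical effect of one early stopper is 0.03-0.07, and no primary endpoint or model-based exposure is touched.

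The percentages assume linear one-compartment kinetics, 14-day intervals, no missed or withheld doses before the sample, and that the half-life from the first-time-in-human study applies in diffuse cutaneous systemic sclerosis. SAP section 16.10.3 leaves the fit of the healthy-volunteer model in these patients to be checked. Treating Day 57 as a trough rests on the SAP display footnote, because only the Day 1 PK sample is marked pre-dose in the schedule. The number of early stoppers is not given, so the extent of mixing is unknown.

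**What to change.** In SAP section 16.5.3, for the final analysis, define measured steady state as the Day 85 (Week 12) trough in participants who received all six doses. Compute the Figure 4.6 coefficient on them. Plot everyone else as marked points, or list them, with the number of doses received. Requiring all six doses matters: a filter on the last two alone would still admit participants with earlier missed or withheld doses and leave the stages mixed.

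For any data cut before Day 85 is available, label the value as the last pre-dose trough, nominally Day 57, and not as steady state.

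The cost is one derivation line, an axis label and a footnote, using samples already scheduled. The downside is that participants with missed or withheld doses leave the main correlation. That loss could be selective if doses were withheld for low platelets, since the plan expects platelet reduction to relate to drug concentration (protocol sections 5.5 and 10.3.2). This is why they should stay visible in the figure. Even Day 85 is only 90-95% of steady state, and the footnote should say so.
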